### 3. OBJECTIVES AND ENDPOINTS

#### 3.1. Objectives and Endpoints: Parts A and B (Healthy Participants)

Objectives	Endpoints
Primary	

 
To evaluate the safety and tolerability of GSK3923868 following single and repeat inhaled administration in healthy participants.
 
	
 
Adverse events (AEs) and serious adverse events (SAEs).
 
Clinically significant laboratory values, vital signs, 12-lead electrocardiogram (ECG) and spirometry measurements up to Day 2 of the final treatment period in Part A, and Day 18 in Part B.
 

Secondary	
Derived pharmacokinetic parameters as data permit, including (but not limited to):
 
Single dose (Part A, Cohorts 1 & 2):
 
 
Area under the plasma GSK3923868 concentration versus time curve from time zero to last quantifiable concentration (<math>AUC(0-t)</math>) and from time zero to infinity (<math>AUC(0-\infty)</math>) (if determined).
 
Maximum observed GSK3923868 plasma concentration (<math>C_{max}</math>).
 
Time to maximum observed plasma drug concentration (<math>T_{max}</math>).
 
 
Repeated dose (Part B, Cohorts 3 & 4):
 
 
<math>AUC(0-\tau)</math> on Day 1 and Day 14 (<math>\tau=24h</math> for once a day dosing regimen) (if determined).
 
<math>C_{max}</math> and <math>T_{max}</math> on Day 1 and Day 14.
 

CCI

Objectives	Endpoints
CCI	

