### 3.2. Objectives and Endpoints: Part C (Participants with Asthma)

Objectives	Endpoints
Primary	

 
To evaluate the safety and tolerability of GSK3923868 following repeat inhaled administration in participants with asthma.
 
	
 
AE and SAEs
 
Clinically significant laboratory values, vital signs, 12-lead ECG and spirometry measurements up to Day 8.
 

Secondary	

 
To evaluate the plasma pharmacokinetics of GSK3923868 following repeat inhaled administration in participants with asthma.
 
	
 
AUC(0-<math>\tau</math>) on Day 1 and Day 7 (<math>\tau=24</math>h for once a day dosing regimen) (if determined).
 
Cmax and Tmax on Day 1 and Day 7.
 

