#### 8.1.5. Clinical Safety Laboratory Assessments

- See [Appendix 2](#) for the list of clinical laboratory tests to be performed and to the SoA for the timing and frequency.
- The Investigator must review the laboratory report, document this review, and record any clinically significant changes occurring during the study as an AE. The laboratory reports must be filed with the source documents.

- In Part C, abnormal laboratory findings associated with the underlying disease are not considered clinically significant, unless judged by the Investigator to be more severe than expected for the participant's condition.
- All laboratory tests with values considered clinically significantly abnormal during participation in the study should be repeated until the values return to normal or baseline or are no longer considered significantly abnormal by the Investigator or Medical Monitor.
  - If clinically significant values do not return to normal/baseline within a period of time judged reasonable by the Investigator, the aetiology should be identified, and the Sponsor notified.
- All protocol-required laboratory tests, as defined in Section 10.2, must be conducted in accordance with the SRM and the SoA (Section 1.3).
- If laboratory values from non-protocol specified laboratory tests performed at the institution's local laboratory require a change in participant management or are considered clinically significant by the Investigator (e.g., SAE or AE or dose modification), then the results may be recorded in the eCRF.

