**9.4.1.2. Laboratory values, vital signs, 12-lead electrocardiogram and Spirometry**

Whilst all data collected will be summarized, only measurements which are clinically significant at any timepoint between randomisation and follow up will be reported as part of the primary endpoint. Potential clinical interest (PCI) ranges will be defined in the SAP.

This data includes:

- Laboratory results for haematology, clinical chemistry and urinalysis (see [Appendix 2](#) for full details).
- Vital Signs measurements for semi supine systolic and diastolic blood pressure, pulse rate, respiratory rate and temperature
- 12-lead safety electrocardiogram (ECG) measurements for heart rate, PR, QRS, QT and QT interval corrected for heart rate according to Frederica's formula (QTcF) intervals
- Spirometry measurements for FEV1 and FVC

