4. STATISTICAL ANALYSES

4.1. General Considerations

4.1.1. General Methodology

The Safety Analysis Set will be used for all outputs except for pharmacokinetic (PK) **CCI** endpoints which will use the Pharmacokinetic Analysis Set.

All cohorts will be presented separately, except Cohorts 3 and 4 which will be combined, unless otherwise stated. In addition, for Part A, all outputs excluding study population will be summarised according to treatment and dose level of GSK3923868.

In the case of wrong stratification assigned at the time of randomization, the analyses will be performed based on the data collected in the eCRF, not the assigned stratum at randomization.

Confidence intervals will use 95% confidence levels for both summary statistics and statistical analysis, unless otherwise stated.

Unless otherwise specified, continuous data will be summarized using descriptive statistics: n, mean, standard deviation (std), median, minimum and maximum. Categorical data will be summarized as the number and percentage of participants in each category.

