4.2.1. Definition of endpoints

Adverse events will be coded using the standard Medical Dictionary for Regulatory Affairs (MedDRA dictionary).

Grade 1 AEs are defined as mild. Grade 2 or higher AEs are defined as moderate or severe. This study will report AEs as mild, moderate or severe.

A study intervention-related AE/SAE is defined as an AE/SAE for which the investigator classifies the possible relationship to study intervention as "Yes". A worst-case scenario approach will be taken to handle missing relatedness data, i.e. the summary table will include events with the relationship to study intervention as 'Yes' or missing.

Spirometry assessments are performed in triplicate with the highest value reported.

Clinically significant values are defined as:

- Values in the potential clinical interest (PCI) ranges for laboratory values, vital signs and ECGs
- Values that achieve the study stopping criteria (protocol section 7.2.5) for spirometry

The same PCI ranges will be used for both healthy volunteers and stable asthmatics, with all ranges being defined in the OPS.

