4.2.2.2. Laboratory Data, Vital Signs, ECGs and Spirometry

For laboratory data, separate tables for haematology, clinical chemistry and urinalysis tests will be produced. Liver biochemical parameters will be included with clinical chemistry tests. Vital signs data will include semi supine systolic and diastolic blood pressure, pulse rate, respiratory rate and temperature measurements.

ECG data will include PR, QRS, QT and QTcF intervals.

Spirometry data will include FEV₁ and FVC measurements.

For haematology, clinical chemistry, urinalysis, vital signs, ECG and spirometry data the following information will be summarised:

1. Clinically significant values at each visit
2. Raw and change from baseline values at each visit

Note: The first table is the only one included as part of the primary endpoint. [redacted]

[redacted]

In order to detect potential bronchospasms, an additional table for spirometry values will be produced which summarises the changes between daily pre- and post-dose FEV₁ and FVC values.

For ECGs, a figure plotting the baseline QTcF and the worst-case post-baseline values will be produced. The figure will have reference lines at 480 and 500 msec for both the ordinate and the abscissa axes. There will be diagonal reference lines at equality (i.e. a 45 degree line), at equality plus 30 msec, and at equality plus 60 msec.

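### The only stated primary-endpoint table for laboratory, vital-sign and ECG data is by visit, so it does not show how many participants ever had a clinically significant value

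*SAP*

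**What the plan says.** SAP Section 4.2.2.2 lists two summaries for haematology, clinical chemistry, urinalysis, vital signs, ECG and spirometry. One is "Clinically significant values at each visit"; the other gives raw values and changes from baseline by visit. A note adds: "The first table is the only one included as part of the primary endpoint". Some text after that note is redacted.

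SAP Section 4.2.1 defines clinical significance value by value: "Values in the potential clinical interest (PCI) ranges for laboratory values, vital signs and ECGs". For spirometry it uses the stopping criterion in protocol Section 7.2.5 instead. SAP Section 4.1.1 sets the general default: "Categorical data will be summarized as the number and percentage of participants in each category".

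Protocol Section 9.4.1.2 states that "only measurements which are clinically significant at any timepoint between randomisation and follow up will be reported as part of the primary endpoint". Protocol Section 3.1 gives a different end of window for Parts A and B ("spirometry measurements up to Day 2 of the final treatment period in Part A, and Day 18 in Part B"), and Section 3.2 does so for Part C ("Clinically significant laboratory values, vital signs, 12-lead ECG and spirometry measurements up to Day 8"). SAP Section 4.2 repeats the windows of Sections 3.1 and 3.2.

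The one worst-case post-baseline display in the visible SAP text is a QTcF figure, and it is not part of the primary endpoint. SAP Section 1 leaves the specification of data displays to the OPS, which is not among the documents supplied.

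**The concern.** A first-in-human safety review asks how many participants on each dose had an abnormality. A table with one row per visit does not answer that. One participant with a persistent abnormality and several participants with one transient abnormality each can produce identical rows, although the safety reading differs.

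The rest of the plan reasons by participant. SAP Section 4.2.2.1 counts participants with any adverse event. Protocol Section 9.4.1.1 counts each participant once, under the maximum severity or strongest relationship. The dose-escalation stopping criteria in protocol Section 6.5.2 count participants who meet the liver, QTc or spirometry criteria. In the visible text, only the measurement half of the primary endpoint lacks a participant-level summary.

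**Working it through.** **The plan's own figures.** SAP Section 5 gives the chance of seeing no adverse event among n participants. The formula is (1 − p)^n.

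| n | p = 5% | p = 20% | Plan states |
|---|---|---|---|
| 5 | 0.95^5 = 0.774 | 0.80^5 = 0.328 | 77%, 33% |
| 9 | 0.95^9 = 0.630 | 0.80^9 = 0.134 | 63%, 13% |
| 12 | 0.95^12 = 0.540 | 0.80^12 = 0.069 | 54%, 7% |

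All six reproduce. They count each participant once and concern adverse events, so they are context and not a calculation for this table.

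**Inputs for the check.**
- Active participants: N = 12 in Part B and 12 in Part C (SAP Section 5).
- Laboratory days after the first dose, Part C schedule: Days 2, 4, 6 and 8, so k = 4.
- Laboratory days after the first dose, Part B schedule as extracted: Days 2, 4, 6, 8, 10, 12, 14, 16 and 18, so k = 9.
- Pattern of flags: one active participant per visit. This is an assumption; the documents give no expected rate.

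**Bounds.** Let c1, …, ck be the participants flagged for a parameter at each visit, and M the number flagged at least once. Then max(c) ≤ M ≤ min(N, sum of c).

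| Setting | Lower bound | Upper bound |
|---|---|---|
| Part C laboratory, k = 4 | 1/12 = 8.3% | min(12, 4) = 4, or 4/12 = 33.3% |
| Part B laboratory, k = 9 | 1/12 = 8.3% | min(12, 9) = 9, or 9/12 = 75.0% |

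The exact 95% intervals are 0.2% to 38.5% for 1/12, 9.9% to 65.1% for 4/12 and 42.8% to 94.5% for 9/12. In Part B the intervals at the two ends do not overlap; in Part C they do.

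**The same point as a risk.** Assume a 5% risk per participant at each visit. If the same participants are affected every time, the any-visit risk stays at 5%. If visits are independent, it is 1 − 0.95^4 = 18.5% over four visits and 1 − 0.95^9 = 37.0% over nine. The 5% is again an assumption.

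**Spirometry.** Here the flag is the stopping criterion. Protocol Section 7.2.5 withdraws a participant who meets it, and Section 7.2.8 bars a restart. A participant should therefore be flagged once, and the visit counts should add up to participants.

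**Window.** Protocol Section 9.4.1.2 runs from randomisation to follow-up. Protocol Sections 3.1 and 3.2 and SAP Section 4.2 stop at Day 2 of the final period (Part A), Day 18 (Part B) or Day 8 (Part C). The follow-up contact is a telephone call with no laboratory, vital-sign or ECG assessment scheduled, so in Parts B and C the difference concerns only unscheduled readings. In Part A Cohort 2 the schedule, as extracted, puts the discharge laboratory sample on Day 3, after the Day 2 cut-off. An any-timepoint count needs one agreed window.

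**The case against.** The strongest reply is that the protocol never asks for a participant count. Sections 3.1, 3.2 and 9.4.1.2 speak of values or measurements, SAP Section 4.2.1 defines significance per value, and a by-visit table reports each such value at its visit. This stands. A reader might infer that the SAP contradicts the protocol's definition of the endpoint; the documents do not support that.

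The OPS and the redacted text may already specify an any-visit row. This also stands, so the point concerns what the visible SAP states and cannot be that no such count is planned. It does not alter the visible note that the by-visit table is the only primary one.

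A reader might infer that events seen at unscheduled repeats are lost. Nothing in the SAP excludes them. Protocol Section 8.1.5 says laboratory values already judged clinically significantly abnormal "should be repeated until the values return to normal or baseline", and Section 7.2.4 asks for two further ECGs only after a single ECG has met the criteria. The triggering reading would normally sit at a scheduled visit. What remains is that the visible SAP mentions unscheduled readings only for baseline (Section 4.1.2) and gives no post-dose rule.

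A reader might also infer that the sample-size argument is undermined. It concerns adverse events, which are counted by participant. Protocol Section 8.1.5 requires clinically significant laboratory changes to be recorded as adverse events, and the definition in Section 10.3.1 covers other clinically significant safety findings. Abnormalities that the investigator judges significant therefore already reach a participant-level output. The gap is narrower: values in a PCI range that the investigator did not judge clinically significant.

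**Conclusion.** The point holds as an improvement to the primary summary for laboratory, vital-sign and ECG data. Visit counts do not determine how many participants had a clinically significant value in the endpoint window; that follows from the bounds alone and needs no assumed rate. The sizes shown, 1 to 4 of 12 in Part C and 1 to 9 of 12 in Part B, rest on an illustrative pattern of one flag per visit and, for Part B, on the schedule as extracted. The upper bounds require a different participant at every visit.

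It is not a contradiction between protocol and SAP, it barely touches spirometry, and it is subject to the OPS and the redacted text. The study tests no hypothesis, so the consequence lies in how the primary safety results can be read.

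**What to change.** First reconcile the window, so that protocol Section 9.4.1.2 agrees with protocol Sections 3.1 and 3.2 and SAP Section 4.2.

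Then amend SAP Section 4.2.2.2 to make the primary summary the number and percentage of participants with at least one clinically significant post-dose value, per parameter, over that window. Present it by treatment and dose, and per treatment period in Part A. State that post-dose unscheduled readings are included. Keep the by-visit table as supportive. If the OPS already specifies such a row, name it in the SAP as the primary summary.

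The cost is one extra row or table per data type. No new data are needed.

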**Footnotes to Part C: Repeat Dose | Asthma (Cohort 5)**

1. Day -1 inhaler training may be performed on Day 1 if needed and before administration of the first dose. Additional training may be provided as needed and according to Investigator discretion.
2. To be performed according to local site procedures. Additional ad hoc testing may be implemented based on local site procedures.
3. Predose and 30 min only.
4. PEF measurements will be taken in triplicate twice each day (once in morning upon waking and once in the evening before bedtime) from Day -1 evening until discharge on Day 8. Clinical site staff will complete and record the PEF measurements at each time point.
5. Provide PEF device refresher training if necessary.
6. Includes systolic and diastolic blood pressure, heart rate, respiration rate and tympanic temperature.
7. Predose only
8. On treatment days ECGs will be collected at predose and 6-hours post-dose. On Day 1 predose, triplicate measurements will be collected, and the mean values will be used to calculate baseline. At all other times single ECGs can be taken.
9. Cardiac telemetry to start approximately 1-hour pre-dose and continuously until 6 hours post dose.
10. Clinical Chemistry and Haematology only.
11. At pre-dose, 5 min, 15 min, 30 min, 45 min, 1 h, 2 h, 4 h, 6 h, 8 h, 12 h and 16 h

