	
the bronchioloalveolar junction at 2060 µg/kg/day. In addition, an increased incidence of inflammatory cell infiltrate (minimal or slight severity), composed predominantly of granulocytes, of the peribronchiolar/perivascular interstitium was also seen at 2060 µg/kg/day. Minimal or slight inflammatory cell infiltrate was seen at a higher than control incidence in females given 2060 µg/kg/day only. However, no microscopic findings in dog IH and rat IV studies.
	
NOAEL exposure margins (AUC: 15-fold; Cmax: 5-fold; lung deposition: 5-fold).
 
Monitoring: respiratory AEs will be monitored and spirometry will be conducted pre- and post-dosing in all three parts of the study. In addition, peak expiratory flow (PEF) monitoring will be implemented for asthmatics in Part C.
 
Sentinel dosing will be used at each dose escalation (Part A), and also for one of the repeat dose cohorts (Part B). Escalation will only proceed after a blinded review of safety, tolerability and plasma PK obtained in at least 5 participants on active treatment at the prior dose level.

Study Procedures		
Spirometry assessments	Shortness of breath, coughing, light headedness or fainting, and/or chest tightness during the spirometry assessments.	As specified in the informed consent form for this study, if any of these symptoms should occur, the participant will receive appropriate medical treatment.
CCI		

Potential Risk of Clinical Significance	Summary of Data/Rationale for Risk	Mitigation Strategy
	CCI	

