### 7.2.6. Asthma Exacerbation Stopping Criteria (Part C Only)

Any participant experiencing an exacerbation of asthma must be withdrawn from the study. An asthma exacerbation is defined as follows:

- Episodes characterised by a progressive increase in symptoms of shortness of breath, cough, wheezing or chest tightness and progressive decrease in lung function, i.e. they represent a change from the patient's usual status that is sufficient to require a change in treatment [[GINA](#), 2020].
- A progressive decrease in lung function is defined as sustained drop in PEF of > 20 % from baseline (Day 1, predose) maintained for  $\geq 3$  days. In the absence of PEF measurements, Investigator judgement will be applied.

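### The readable SAP names no summary of the twice-daily Part C peak flow, the only scheduled same-day lung-function reading after 30 minutes post-dose

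*SAP*

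**What the plan says.** **Protocol, collection.** The Part C schedule of activities (section 1.3, footnote 4) calls for three PEF blows each morning on waking and each evening before bed, "from Day -1 evening until discharge on Day 8". It adds that "Clinical site staff will complete and record the PEF measurements at each time point". Footnote 3 sets spirometry on Days 1 to 7 at "Predose and 30 min only", and the schedule adds one spirometry assessment on Day 8.

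**Protocol, purpose.** In the risk table (section 2.3.1), the row on respiratory tract irritancy says that "peak expiratory flow (PEF) monitoring will be implemented for asthmatics in Part C". Section 7.2.6 uses PEF for the lung-function part of the asthma exacerbation definition: a "sustained drop in PEF of > 20 % from baseline (Day 1, predose) maintained for" at least 3 days.

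**SAP, analysis.** Section 4.2.1 defines a clinically significant spirometry value by reference to protocol 7.2.5, an FEV1 rule, and does not refer to 7.2.6. Section 4.2.2.2 limits spirometry data to FEV1 and FVC. Its list of summarised data types does not include PEF. The further display that begins "In order to detect potential bronchospasms, an additional table for spirometry values will be produced" shows daily pre- to post-dose change in FEV1 and FVC.

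**Statements that may bear on it.** Protocol 9.4.1.2 promises a summary of everything collected, then lists FEV1 and FVC but not PEF. SAP 1 defers the specification of displays to the Output and Programming Specification (OPS). SAP 4.2.2.2 contains redacted lines. SAP 4.7 declares no change from the protocol.

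**The concern.** Safety and tolerability is the primary objective of Part C, and protocol 4.2 says the placebo arm is there to help separate treatment effects from other events. For an inhaled drug given once daily to people with asthma, a fall in lung function some hours after dosing is a plausible tolerability signal. The schedule contains a measurement that could show it, the evening PEF, but the visible analysis plan gives that measurement no table.

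If the visible lists are followed as they stand, measured evening declines would not be set out by treatment in the study report. They would reach it only indirectly, if the fall persisted to the next morning's spirometry or was recorded as an adverse event.

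**Working it through.** **The plan's own Part C figure.** The SAP gives no number for PEF. Its only numerical support for Part C is the chance of seeing no event among 12 active participants. This reproduces: 0.95^12 = 0.540 (stated 54%) and 0.80^12 = 0.069 (stated 7%). It is not in dispute.

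**Scheduled lung-function sessions per Part C participant** (from the Part C schedule, footnotes 3 and 4, taking Day 8 discharge to fall after the morning reading and before the evening one):

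| Measure | Count | Named summary in readable SAP |
|---|---|---|
| Spirometry (FEV1, FVC) | 7 days × 2 + 1 (Day 8) = 15 | Yes |
| PEF | 1 (Day -1 evening) + 7 days × 2 + 1 (Day 8 morning) = 16 | No |

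**The PEF sets that nothing else duplicates.** Waking PEF falls close to predose spirometry on most days, so it adds little timing information. The evening sets on dosing days do add some:

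- per participant: 7 (Days 1 to 7)
- all participants: 7 × 16 = 112
- active: 7 × 12 = 84
- placebo: 7 × 4 = 28

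**Spacing of readings.** With dosing every 24 h, the 30-minute spirometry and the next day's predose spirometry are about 24 − 0.5 = 23.5 h apart. The evening PEF is the only scheduled lung-function reading on the same day inside that interval. Clock times are not in the documents. Assuming dosing at 08:00 to 10:00, a bedtime reading at 20:00 to 23:00 and waking at 06:00 to 08:00, including PEF would shorten the longest interval to between 10 h (dose 10:00, evening 20:00, waking 06:00) and 14.5 h (dose 08:00, evening 23:00).

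**What a named table would and would not show:**

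- Fall present at 30 minutes: shown in the daily pre- to post-dose FEV1/FVC table.
- Fall that lasts to the next morning: shown in FEV1/FVC change from baseline at each visit.
- Fall recorded as an adverse event, or leading to discontinuation because of one: shown in the tables of SAP 4.2.2.1.
- Evening fall that recovers by the next predose spirometry and is not recorded as an adverse event: shown in no named table.

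**Related mismatch.** SAP 4.2.1 takes its clinically significant spirometry value from protocol 7.2.5, which is set at 1 hour post-dose. The Part C schedule has spirometry at 30 minutes and none at 1 hour. The primary-endpoint spirometry flag therefore has no matching scheduled time in Part C.

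**The case against.** The strongest reply is that absence from the plan is not proved. SAP 4.2.2.2 has redacted lines just before the bronchospasm table, immediately after the note on which tables are primary, where a supportive display could sit. The OPS is not available. Protocol 9.4.1.2 promises that everything collected is summarised, and SAP 4.7 reports no departure from the protocol. This stands as a limit on the point. A reader might infer that the SAP analyses no PEF at all, and the documents do not support that. They support only that the unredacted variable definitions and summary lists, which read as complete sentences, leave it out.

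A second reply is that a reader might infer that reported lung function is blind for 23.5 of every 24 hours. That goes too far. Predose FEV1 and FVC are summarised every day, any spot schedule leaves most hours unmeasured, and the investigator sees PEF as it is recorded. Worsening asthma can also reach the adverse event tables, although protocol Appendix 3 excludes expected signs of the disease under study unless they are more severe than expected. What is left uncovered is the transient, unreported evening fall.

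Third, PEF is not a listed Part C endpoint, no hypothesis is tested, and there are only 4 placebo participants, 2 per stratum. All of this is correct. It means that the display should be supportive and descriptive, and it does not argue against having one.

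**Conclusion.** The point holds as an omitted supportive safety summary. The protocol collects PEF for respiratory safety and uses it in a withdrawal definition, and the readable SAP names no display of it. The gap affects 7 evening sets per participant (112 in all, 84 on active) and one kind of signal: an evening fall that recovers by the next predose spirometry and is not recorded as an adverse event. No sample size, probability or primary-endpoint figure changes.

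The conclusion rests on two assumptions: that the redacted lines and the OPS contain no PEF display, and that Part C spirometry is done at the scheduled 30 minutes. If the OPS already specifies a PEF table, one sentence in the SAP saying so would settle the matter.

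A reader might also take any single PEF fall of more than 20% as meeting protocol 7.2.6. It does not. That definition needs the fall to be measured from Day 1 predose and sustained for at least 3 days, and an exacerbation also needs worsening symptoms.

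**What to change.** Add to SAP 4.2.2.2, for Part C only and labelled supportive and outside the primary endpoint:

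1. PEF by treatment and day, morning and evening separately, using the best of the three blows. The SAP states a triplicate rule for spirometry only, so the PEF rule has to be written down.
2. Raw values and change from baseline, with the protocol's Day 1 predose value as baseline. For evening readings, also show change from the Day -1 evening value as a descriptive time-matched reference.
3. The number of participants meeting the existing PEF definition in protocol 7.2.6. Any count of single readings with a fall above 20% should be labelled descriptive and not described as meeting 7.2.6.

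If the sponsor prefers to list PEF without summarising it, the SAP should say so and give the reason.

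The cost is one or two tables from data that site staff already record, with no new assessments. Precision will be limited with 12 active and 4 placebo participants, so the tables should be read as description only. None of this alters a withdrawal rule.

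Separately, protocol 7.2.5 (1 hour post-dose) and the Part C spirometry schedule (30 minutes) must be reconciled, and SAP 4.2.1 should then refer to a time at which Part C spirometry is scheduled.

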### 6.5.2. Dose Escalation Stopping Criteria

Further dosing at the current dose level stops and that dose and no higher dose may be used if any of the following occur:

- Any one participant experiences a serious adverse event that is considered at least possibly related to the study drug.
- Two participants experience a severe adverse event or bronchospasm that is considered at least possibly related to the study drug.
- Three participants meet liver chemistry stopping criteria outlined in Section [7.2.3](#).
- Three participants meet QTc stopping criteria outlined in Section [7.2.4](#).
- Three participants meet spirometry stopping criteria outlined in Section [7.2.5](#).
- Three participants experience any adverse event considered clinically important by the Investigator.

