### 7.2.5. Spirometry Stopping Criteria

Any participant experiencing a reduction in FEV1 at the 1-hour post-dose time point compared to daily predose value of > 25% in Parts A and B and > 20% in Part C will be withdrawn from the study.

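### The SAP's table for detecting potential bronchospasm states neither the scale of change nor any participant count, so the number of participants with a fall below the stopping threshold cannot be determined from it

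*SAP*

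**What the plan says.** SAP 4.2.2.2 lists two outputs for all safety measurements: clinically significant values by visit, and raw and change-from-baseline values by visit. For spirometry (FEV1 and FVC) it adds a third: "In order to detect potential bronchospasms, an additional table for spirometry values will be produced which summarises the changes between daily pre- and post-dose". The scale of change, categories, participant counts and a listing are not mentioned.

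Where nothing else is specified, SAP 4.1.1 applies: "continuous data will be summarized using descriptive statistics: n, mean, standard deviation (std), median, minimum and maximum".

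The event display is the first output, "Clinically significant values at each visit". For spirometry, SAP 4.2.1 defines clinically significant as "Values that achieve the study stopping criteria (protocol section 7.2.5) for spirometry". Protocol 7.2.5 sets that criterion as a fall in FEV1 at 1 hour post-dose, "compared to daily predose value of > 25% in Parts A and B and > 20% in Part C". It contains no FVC criterion.

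Protocol 6.5.2 counts participants when it stops escalation. One trigger is "Three participants meet spirometry stopping criteria". A separate trigger is two participants with a severe adverse event or bronchospasm at least possibly related to study drug.

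**The concern.** The table has a stated purpose, and that purpose concerns individuals. Bronchospasm happens to a participant. It is the first drug risk listed in Protocol 2.3.1, and respiratory tolerability is part of the primary objective. A reader of the study report will want to know how many participants at a dose had a noticeable same-day fall, and how large each fall was relative to that participant's own predose value. A summary of changes with an unstated scale supplies neither.

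Falls that reach the 7.2.5 threshold have their own table. What is at stake is the range below it, meaning FEV1 falls up to 25% in Parts A and B and up to 20% in Part C, and FVC falls of any size. With 9 active participants per dose in Part A and 12 in each of Parts B and C, a few moderate falls would be informative for later studies in patients with airway disease.

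The same SAP section treats QTcF differently. It plots each baseline against the worst post-baseline value, with reference lines at 480 and 500 msec and at increases of 30 and 60 msec. The limits in Protocol 7.2.4 are above 500 msec and above 60 msec, so sub-threshold levels are marked for QTcF. Spirometry has no equivalent.

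**Working it through.** **The plan's nearest figures.** The plan gives no figure for spirometry falls. Its only related calculation (Protocol 9.2, SAP 5) is the chance of seeing no participant with an adverse event, (1 − p)^n:
- n = 9: 0.95^9 = 0.630 and 0.80^9 = 0.134 (stated 63% and 13%).
- n = 12: 0.95^12 = 0.540 and 0.80^12 = 0.069 (stated 54% and 7%).

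Both reproduce. They show that the plan's own safety reasoning is about numbers of participants with an event.

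**Do the default statistics determine the count?** Take n = 12 active participants (Parts B and C). Assume the change is already in percent, which is the reading kinder to the plan. Assume a cut-off of a fall of at least 10%; the documents define none. Three constructed data sets, in percent:

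- Set 1: −16, −14, −9, −9, −9, −1, 0, 0, 1, 3, 5, 6
- Set 2: −16, −14, −12, −10, −4, −1, 0, 1, 2, 2, 3, 6
- Set 3: −16, −12, −10, −10, −10, −1, 0, 1, 2, 3, 4, 6

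Each set sums to −43 and has a sum of squares of 767. For all three:
- mean = −43/12 = −3.58
- SD = √[(767 − 43²/12)/11] = √(612.9/11) = 7.47
- median = (−1 + 0)/2 = −0.5
- minimum = −16, maximum = 6

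The participants with a fall of at least 10% number 2, 4 and 5. No fall exceeds 20% or 25%, so the clinically significant table shows 0 in every case. The two tables together cannot tell 2 of 12 from 5 of 12.

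**What the mean and minimum show.** One 18% fall with all other changes at zero moves the mean by 18/12 = 1.5 points (n = 12) or 18/9 = 2.0 points (n = 9). The mean barely registers it, but the minimum does. The table therefore shows the worst single change but not how many participants lie near it.

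**If the change is in litres.** The minimum then does not give a percentage either. With assumed predose values, a 0.5 L fall is 0.5/2.0 = 25%, 0.5/2.5 = 20%, 0.5/4.0 = 12.5% or 0.5/5.0 = 10%. This is a second gap, and it arises only on that reading.

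**Repeated days.** Part C measures predose and post-dose spirometry on seven dosing days. Seven daily minima do not show whether one participant fell repeatedly or several fell once each.

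**The event table in Part C.** Protocol 7.2.5 refers to the 1-hour post-dose value. The Part C Schedule of Activities takes dosing-day spirometry at predose and 30 minutes only. Read literally, no scheduled Part C value can enter the clinically significant spirometry table.

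**The case against.** The case for leaving the SAP alone has several sound parts.

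- **Bronchospasm is counted elsewhere.** Protocol 7.2.5 does not mention bronchospasm, and 6.5.2 lists it apart from the spirometry criterion. Bronchospasm reported as an adverse event is tabulated by preferred term (Protocol 9.4.1.1, SAP 4.2.2.1). A reader might infer that bronchospasm goes uncounted; the documents do not support that. The spirometry table is a supplementary screen.
- **The table is not blind to individuals.** The default includes the minimum. A reader might infer that a single severe fall would be hidden in a mean, but it would not be.
- **The scale is unstated, not wrong.** A reader might infer that changes will be in litres. The SAP does not say so, and the same-day comparison is the one that 7.2.5 expresses in percent.
- **Detail may exist out of sight.** SAP 1 sends the specification of data displays to the Output and Programming Specification, and text next to this sentence is blacked out. It would go too far to say that the report will be unable to give the count.
- **The consequence is limited.** Only the clinically significant table belongs to the primary endpoint, no hypothesis is tested, and dose decisions rest on emerging safety review.

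All of this stands and narrows the point, but it does not remove it. The scale of change and the event to be counted are analysis definitions rather than layout: the SAP itself defines the spirometry event in 4.2.1 while leaving the ranges for the other measurements to the specification. Protocol 6.3 also allows selected sponsor staff to see unblinded safety data as each cohort completes, so cut-offs are best fixed in advance.

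**Conclusion.** The point holds as a gap in specification. On the visible text, the bronchospasm table has no stated scale and no participant count. Under the default statistics, the number of participants with a fall smaller than the 7.2.5 threshold cannot be determined, and no other visible SAP output gives it. The same is true of FVC falls of any size, because 7.2.5 covers FEV1 only.

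The illustration gives the size: identical summaries are compatible with 2, 4 or 5 of 12 participants. It rests on constructed data and an assumed 10% cut-off, and it does not depend on the litre reading. It shows what the summary leaves open and does not predict this trial's data.

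The effect is on how well the report describes airway tolerability. The primary endpoint table and the trial's stopping decisions are not affected by this gap. The Part C time-point mismatch is separate, but until it is resolved more weight falls on this table for Part C.

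**What to change.** In SAP 4.2.2.2, define the bronchospasm table on percent change from the same-day predose value. By treatment and dose, keep the descriptive statistics and add the number and percentage of participants in a few pre-specified categories of worst same-day fall in FEV1, and likewise FVC. Give these at any time on treatment, and by day where measured. The cut-offs (for example 10%, 15%, 20% and 25%) are for the sponsor to choose. They are reporting categories only and change no withdrawal or stopping rule.

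The cost is SAP text and table rows; no data, visits or participants are added. Four cut-offs for two measures make 8 rows at any time on treatment. Adding seven dosing days in Part C makes 4 × 2 × 8 = 64 rows, so fewer categories by day would be reasonable. Low categories will include normal variation, and placebo calibrates this only roughly, with 4 participants in each of Parts B and C. If 30% of placebo participants crossed a low cut-off by chance (an assumption), none of four would do so with probability 0.7^4 = 24%.

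Separately, the sponsor should reconcile the 1-hour time point in Protocol 7.2.5 with the predose and 30-minute spirometry in the Part C schedule, so that it is clear which Part C values can count as clinically significant.
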